5.6 Data Quality Assurance

[Redacted]

[Redacted]

[Redacted]

[Redacted]

[Redacted]

[Redacted]

5.6.2 Database Management and Quality Control

The study will be monitored by the Clinical Monitor, and/or representatives of CLINUVEL, or its delegated representative, as frequently as is necessary to determine that data recording and protocol adherence are satisfactory. [REDACTED]

The detailed procedures for data entry, data coding, cleaning and electronic data transfer will be provided in the Data Management Plan.

5.7 Statistical Methods, Exploratory Statistics

[REDACTED]

Descriptive and exploratory statistics (non-parametric analyses) will be performed [REDACTED]

5.7.2 Efficacy Assessment

5.7.2.1 Specification of Efficacy Endpoints

Primary Endpoints

- (i) *Evaluate the safety of afamelanotide* by monitoring and recording TEAEs (on all days of administration and up to day 42).
TEAEs will be recorded and coded as MedDRA Preferred Terms.

Secondary Endpoints

- (i) *Evaluate changes in the reperfusion of the ischaemic core and the penumbral ischaemic zone* (salvageable tissue) by quantitative analysis of hemodynamics:

[REDACTED]

- [REDACTED]
- [REDACTED]
- [REDACTED]

Upon completion of the study, each patient will generate efficacy after comparing the DWI-FLAIR on Days 3(\pm 1) and 9(\pm 1) with the CTP on Day 0 (Day of Admission).

[REDACTED]

[REDACTED]

[REDACTED]

[REDACTED]

[REDACTED]

5.7.3 *Safety Assessment*

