To be eligible to enter the study, patients must meet the following *inclusion criteria*:

- Male or female subjects with a diagnosis of first AIS due to distal [M2 segment and beyond] occlusion or perforator occlusion
- [REDACTED]
- Mild to moderate stroke severity [REDACTED]
- [REDACTED]
- Aged 18- 85 years
- Written informed consent obtained from patient and/or medical treatment decision maker prior to study-start (upon admission).

To be eligible to enter the study, patients must not meet any of the following *exclusion criteria*:

- Administration of intravenous thrombolytic therapy in distal occlusion as etiology of AIS
- Intervention by endovascular thrombectomy (EVT)
- [REDACTED]
- Any evidence of hepatic (defined as three times standard range) or [REDACTED]
- [REDACTED]
- [REDACTED]
- [REDACTED]
- [REDACTED]
- [REDACTED]
- [REDACTED]
- [REDACTED]

Test product:

Afamelanotide [REDACTED]

Dose: [REDACTED]

Mode of administration: Subcutaneous administration

Reference therapy:

None

Study Endpoints:**Primary Endpoints**

(i) Evaluate the safety of afamelanotide by monitoring and recording treatment-emergent adverse events (TEAEs) (on all days of administration and up to day 42).

Secondary Endpoints

- (i) Evaluate changes in reperfusion of the ischaemic core and the penumbral ischaemic zone (salvageable tissue)
- (ii) Evaluate neurological functions, cognitive functions, daily activities

Statistical Methods (exploratory):**Primary Endpoints****Safety Analyses:**

The number of participants with TEAEs will be summarized by Medical Dictionary for Regulatory Activities (MedDRA) preferred term and body system. TEAEs will be further summarized by intensity, seriousness, outcome and relationship to study drug. Participants who prematurely terminate treatment due to AEs related to study medication will be summarized.

Secondary Endpoints

An evaluation will be made of *changes in the reperfusion of the ischaemic core and the penumbral ischaemic zone* (salvageable tissue) [REDACTED]

In this exploratory analysis, the null hypothesis is formulated as:

H₀: there is no change to the ischaemic core and or penumbral ischaemic zone following the administration of afamelanotide 16mg.

Following changes observed from cerebral imaging, standard clinical outcomes will be monitored.

An evaluation will be made of

- (1) changes of neurological function as measured by NIHSS on Days 1, 2, 7 and 42 compared to baseline

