5.5.3.1.1 Evaluation of MRI imaging (CTP and DWI-FLAIR)

Background

For patients with acute arterial occlusion,

[REDACTED]

[REDACTED]

MRI diffusion weighted imaging (DWI) is accurate in the identification of acutely infarcted tissue.

[REDACTED]

Imaging Protocol

Standard care multimodal computed tomography (CT) will be performed on Day 0. [REDACTED]

[REDACTED]

MRI will be performed at Days 3(\pm 1) and 9(\pm 1) [REDACTED]

[REDACTED]

Efficacy of treatment

[REDACTED]

[REDACTED]

[REDACTED]

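### The stated efficacy comparison (follow-up DWI-FLAIR against Day 0 CTP) measures tissue fate across two modalities and does not by itself support a conclusion about reperfusion

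*Combined protocol and SAP*

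**What the plan says.** Section 5.7.2.1, secondary endpoint (i), is a change in reperfusion of the ischaemic core and penumbra, assessed "by quantitative analysis of hemodynamics". The text directly after that phrase is redacted. Section 4.2 and the synopsis also word the imaging aim as reperfusion.

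A complete, unredacted sentence in section 5.7.2.1 then gives the operative comparison: "each patient will generate efficacy after comparing the DWI-FLAIR on Days" 3(±1) and 9(±1), with CTP on Day 0 as the comparator.

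On what the scans show, section 5.5.3.1.1 states that "MRI diffusion weighted imaging (DWI) is accurate in the identification of acutely infarcted tissue". Its heading names CTP and DWI-FLAIR only. It schedules the CT ("Standard care multimodal computed tomography (CT) will be performed on Day 0") and places MRI at the two follow-up times; the rest of the MRI sentence is redacted.

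The null hypothesis in the synopsis is that "there is no change to the ischaemic core and or penumbral ischaemic zone following the administration of afamelanotide 16mg". The synopsis treats two-sided 0.05 as the significance level, and section 5.7 says the analyses are non-parametric. Section 5.7.4 plans six patients, a number based on availability. Section 5.3.2 has one treatment group.

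**The concern.** A change in perfusion needs a perfusion value at both times. The visible comparison has one at Day 0 only; the follow-up side is a map of infarct. What comes out is how much tissue died or was spared. Sparing can occur without any change in blood flow: the rationale in section 3.0 itself allows for neuroprotection that limits infarct size directly. Reporting the result as reperfusion would therefore attribute a tissue outcome to a mechanism that this comparison did not measure.

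The second problem is the mix of modalities. A core change formed as the follow-up DWI lesion minus the Day 0 CTP core contains both biological change and any systematic difference between the two methods. With no control arm, no between-group contrast can remove that difference. If the change is tested at 0.05, the offset can appear as a change following the drug.

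**Working it through.** **Wording against measurement**

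| Item | Where | Content |
|---|---|---|
| Endpoint label | 5.7.2.1, 4.2, synopsis | Reperfusion of core and penumbra; haemodynamic analysis (5.7.2.1) |
| Baseline scan | 5.7.2.1, 5.5.3.1.1 | CTP within Day 0 CT: perfusion |
| Follow-up scan | 5.7.2.1, 5.5.3.1.1 | DWI-FLAIR on MRI at Days 3(±1) and 9(±1): infarct |
| H0 | Synopsis | No change in tissue zones; perfusion is not mentioned |

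The two scans yield two quantities:

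- infarct growth = follow-up DWI lesion − Day 0 CTP core;
- penumbral salvage = Day 0 CTP penumbra that is not infarcted on follow-up DWI.

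Both bear on H0. Neither contains a follow-up perfusion value.

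**Size of the offset problem**

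The plan has no figure to reproduce: it gives no effect size, SD, power or offset. The following is an illustration for the core difference.

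Inputs from the documents: n = 6; two-sided 0.05; non-parametric analysis; single arm. Assumptions: an exact Wilcoxon signed-rank test; independent, normally distributed paired differences without ties; no true change; a constant modality offset of d SDs of the paired difference.

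1. With n = 6 there are 2^6 = 64 equally likely sign patterns under the null. The smallest two-sided p is 2/64 = 0.03125 and the next is 4/64 = 0.0625. The test therefore reaches 0.05 only when all six differences have the same sign.
2. With offset d, each difference is positive with probability Φ(d), so P(reject) = Φ(d)^6 + [1 − Φ(d)]^6.
3. Results:

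| d (SD) | Φ(d) | P(reject), no true change |
|---|---|---|
| 0 | 0.5000 | 3.1% |
| 0.25 | 0.5987 | 5.0% |
| 0.5 | 0.6915 | 11.0% |
| 1.0 | 0.8413 | 35.5% |

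For d = 0.5: 0.6915^6 + 0.3085^6 = 0.1093 + 0.0009 = 0.1102. Larger assumed offsets give 66.0% (1.5 SD) and 87.1% (2.0 SD).

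4. With five evaluable patients the smallest two-sided p is 2/32 = 0.0625, so this test could not reject. Withdrawn patients are not replaced (5.2.4), so the rates in the table apply only if all six patients have a usable pair of scans.

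**The case against.** The strongest objection is redaction. The text after the mention of haemodynamics, several blocks after the efficacy sentence, the end of the MRI schedule and the whole paragraph on efficacy of treatment in section 5.5.3.1.1 are hidden. Section 5.1 refers to radiological evaluation by CTP with no day visible, and section 3.0 notes that perfusion imaging can be done by CT or MRI. A reader might infer that the trial has no follow-up perfusion measure and cannot address reperfusion at all. The documents do not support that: such a measure can be neither confirmed nor excluded. This objection stands and limits the point to the comparison that is visible. It does not remove the point, because that comparison is stated in full as the one that generates efficacy.

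Other objections also stand in part:

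- **H0.** It mentions neither reperfusion nor haemodynamics. It concerns tissue zones, which the comparison does address, so its wording needs no change.
- **Penumbra.** A reader might infer that the penumbra has no post-dose counterpart. It has one, in the form of salvage.
- **Day 3 to Day 9 change.** Using DWI-FLAIR at both times looks like a clean same-modality substitute. But eligibility is reviewed on Day 0 before medication (1.3) and administration is tied to 24 hours from onset or last seen well (5.3.3), so both MRIs follow the start of treatment. This change has no pre-dose baseline and cannot replace the baseline comparison.
- **Magnitude.** The existence, direction and size of the offset, and the specific test, are assumptions. At 0.25 SD the rejection rate only equals the nominal 5%. It is also not visible whether the raw CTP-to-DWI difference will be tested.
- **Impact.** The endpoint is secondary and exploratory in a six-patient study whose primary objective is safety. This limits the seriousness, but not the need for the label to match the measurement.

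**Conclusion.** The concern holds in a limited form. Taken alone, the stated comparison supports a conclusion about tissue fate and not one about reperfusion or haemodynamics. This follows from the protocol's own description of DWI and needs no outside assumption.

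The offset problem is real in kind, because a single arm gives no means of separating a method difference from a biological one. Its size is unknown. Under the assumptions stated, false rejection runs from 3.1% with no offset to 35.5% at 1.0 SD. These figures show sensitivity and do not estimate the trial's actual error rate.

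The change is worth making because it alters what the imaging results can be said to show, but it does not affect the primary safety objective.

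**What to change.** 1. In section 5.7.2.1, the synopsis and section 4.2, label the result of this comparison as infarct growth (follow-up DWI lesion minus Day 0 CTP core) and penumbral salvage (Day 0 CTP penumbra not infarcted on follow-up DWI). Keep the terms reperfusion and hemodynamics only for a comparison that uses a post-dose perfusion map. If the redacted text already specifies one, the efficacy sentence should refer to it.
2. Leave the wording of H0 as it is. Report raw CTP-to-DWI differences descriptively, with the modality offset stated as a limitation, and do not test them at 0.05 as a drug-related change.
3. Day 3-to-Day 9 DWI-FLAIR change may be added as a same-modality supplement, not as a replacement for the baseline comparison.

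Cost: changes to the endpoint wording and the analysis text, with no new scan or reader. The downside is that no claim of improved reperfusion, and no p-value for the raw cross-modality change, can come from this comparison.

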5.7.3.1 Specification of Safety Endpoint (Primary Endpoint)

The safety endpoint will be the incidence of TEAEs occurring during the study period, including clinically significant changes in laboratory parameters, will be listed by intensity, seriousness, outcome, and relationship to study drug.

5.7.4 *Sample Size*

While this is a phase IIa study of common indication, the sample size is based on availability of patients. A total of six (6) patients are planned to be enrolled in this study. This constitutes an open-label exploratory study.

5.7.5 *Analysis Plan*

5.7.5.1 Safety Population

The Safety Population will include all enrolled patients. Patients screened but not enrolled will be shown in separate listings.

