5.0 INVESTIGATIONAL PLAN

5.1 Overall Design and Plan of the Study

This is an open label phase IIa pilot study to be conducted in six (6) patients with acute AIS during a 6-weeks period [REDACTED]

To determine eligibility for entry into the study, [REDACTED]
[REDACTED] Eligible patients will be enrolled and will be administered [REDACTED]
[REDACTED]

[REDACTED]

[REDACTED]

The results will be reviewed on the basis of a benefit: risk assessment. If the benefit: risk assessment is in favour of afamelanotide, in the opinion of the Investigator, [REDACTED]

Radiological evaluation by assessing the imaging from Computed Tomography Perfusion (CTP)

Clinical evaluations will be performed by accredited study staff over the course of the study. The NIHSS will be performed at the Day of Admission (Day 0) and on Days 1, 2, 3, 4, 7, 8 and 42 or Premature Termination Visit (if applicable). The modified Rankin Scale (mRS) will be performed on Days 0, 7 and 42 or Premature Termination Visit (if applicable). [REDACTED]

Safety assessments (review of AEs and concomitant medications) will be carried out each day (each study visit from the Day of Admission to Day 8 and Day 42 or Premature Termination Visit).

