5.2 Selection of Study Population

The target population consists of male and female patients with AIS due to acute distal (M2 and beyond) large vessel occlusion (LVO) or perforator occlusion and who are ineligible to receive IVT or EVT. The following inclusion and exclusion criteria must be met by each patient before enrollment in the study.

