5.2.1 Inclusion Criteria

The patients have to fulfill all of the following *inclusion criteria* for study participation:

5.2.4 *Withdrawals and Replacement of Patients*

A discontinuation occurs when a patient does not complete the study as required by the study protocol. Patients will be free to discontinue their participation in this trial at any time for any reason. In addition, patients may be withdrawn from the trial at the discretion of the Investigator or medically qualified nominee. A patient may be withdrawn for any of, but not limited to, the following reasons:

- Informed consent withdrawn by the patient or medical treatment decision maker;
- AE requiring study discontinuation;
- When the Investigator's or nominee's best professional judgment would indicate that it would be in the patient's best interest to be withdrawn;
- Violation of inclusion/exclusion requirements.

The reasons for withdrawal or discontinuation of a patient will be recorded in the patient's medical notes and CRF. If an AE is the reason for discontinuation, the event must be followed up and documented as described in the 5.5.3.2 Safety variables of the protocol. If the patient discontinued for any reason after the enrolment into the study, a study Premature Termination visit, as described in 5.5.1, should be performed at the time of study discontinuation, or as soon as possible after discontinuation. This visit will be documented in the patient's medical notes and CRF.

Any patient(s) withdrawn from the trial prior to their completion for any reason will not be replaced. Data compiled to the point of discontinuation will be used for 'intent to treat' (ITT) analysis. Patients violating any of the inclusion and exclusion criteria will be described as protocol deviators.

5.3 **Study Medication**

5.3.1 *Description of Study Medication*

[REDACTED] afamelanotide
[REDACTED]
[REDACTED]

5.3.2 *Treatment Groups*

There is one treatment group in this study (Open-label study). As such, all patients who satisfy the inclusion/exclusion criteria will be allocated a study subject number and receive afamelanotide. Study subject number allocation will be detailed in the CUV801 Study Operating Manual (SOM).

The groups consist of:

- **Six (6) stroke patients with acute distal (M2 and beyond) LVO or perforator occlusion.**

Open label study: Six (6) patients receiving afamelanotide.

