5.7.5.2 ITT Population

The ITT population will include all treated patients, who provide at least one post dose efficacy assessment. This will be the main population for all efficacy analyses.

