5.7.5.7 Safety

Descriptive methods will be used to summarize the safety data. These will be based upon the safety population.

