5.7.5.8 Adverse Events

All AEs, including non-TEAEs, will be listed. A TEAE is defined as:

- An event that was not present prior to or on the day of the first study medication administration but was present after study medication was administered.
- An event that was present prior to first administration of study medication and continued to occur after the administration of the first dose at an increased level of severity.

[REDACTED]

- An event that was present prior to administration of study medication and was documented as completely resolved and re-emerged after the administration of the first dose.

The MedDRA AE dictionary will be used to map verbatim AE terms to preferred terms and body systems. The number of patients with TEAEs will be summarized by preferred term and body system. TEAEs will be further summarized by intensity, seriousness and relationship to study medication. The number of patients who terminate treatment early due to AEs related to study medication will be tabulated. Summaries of the incidence of toxicities will be prepared, as appropriate.

SAEs, SUSARs, and AEs of special interest will be listed individually. Any SAE that occurs prior to the first dose of the study medication, will be documented in the study report.

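### The Safety Population is defined by enrolment rather than receipt of afamelanotide, so an enrolled but undosed patient would dilute the primary TEAE incidence

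*Combined protocol and SAP*

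**What the plan says.** Section 5.7.5.1 defines the set used for safety: "The Safety Population will include all enrolled patients". The only group it sets apart is patients who were screened and not enrolled. It says nothing about patients who were enrolled and not dosed.

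Section 5.7.3.1 specifies the primary endpoint: "The safety endpoint will be the incidence of TEAEs occurring during the study period". Section 5.7.5.7 says of the safety summaries: "These will be based upon the safety population".

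The TEAE definition in Section 5.7.5.8 depends on exposure. Its first limb covers an event that was absent beforehand "but was present after study medication was administered". The other visible limbs cover worsening, or re-emergence, after the first dose.

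For efficacy the plan uses a different word. Section 5.7.5.2 begins: "The ITT population will include all treated patients", and adds a requirement for a post-dose efficacy assessment. On withdrawals, Section 5.2.4 states: "Any patient(s) withdrawn from the trial prior to their completion for any reason will not be replaced".

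**The concern.** The numerator and denominator of the primary endpoint follow different rules: a dose is needed for the first but not for the second. A patient who enrols and leaves before the first dose, for example because consent is withdrawn or a clinical event intervenes, cannot have a TEAE yet remains in the Safety Population. Because withdrawn patients are not replaced, that patient also takes one of only six places.

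If at least one dosed patient has a TEAE, the error can only lower the reported incidence and so make the drug look safer. A table headed N = 6 would also overstate how many patients were exposed. The plan does distinguish treated from enrolled patients, but it applies the exposure-based term to efficacy and not to safety.

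**Working it through.** **Inputs**
- Planned enrolment: 6 patients in one arm, set by patient availability (Section 5.7.4). There is no power or precision calculation to reproduce.
- Denominator as written: all enrolled patients (Sections 5.7.5.1 and 5.7.5.7).
- Numerator: k patients with at least one TEAE, all of whom must have been dosed (Section 5.7.5.8).
- u = number enrolled but never dosed. The documents give no value, so u = 0, 1 and 2 are assumptions.

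**Can u exceed zero under the visible text?** Section 5.1 names two steps: "Eligible patients will be enrolled and will be administered". Section 5.7.5.8 provides for serious adverse events before the first dose, so a pre-dose interval is foreseen. Section 5.2.4 allows withdrawal at any time and does not tie it to dosing. A patient who fails the criteria should not be counted here, because under Section 5.2 the criteria "must be met by each patient before enrollment in the study"; that patient belongs with those screened and not enrolled.

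**Effect on the percentage when k ≥ 1**

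Reported incidence = k/6. Incidence among dosed patients = k/(6 − u). The ratio is (k/6) ÷ (k/(6 − u)) = (6 − u)/6.

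| u (assumed) | Ratio | Relative understatement | Example, k = 2: reported | Example, k = 2: dosed only |
|---|---|---|---|---|
| 0 | 6/6 = 1.000 | none | 2/6 = 33.3% | 2/6 = 33.3% |
| 1 | 5/6 = 0.833 | 16.7% | 2/6 = 33.3% | 2/5 = 40.0% |
| 2 | 4/6 = 0.667 | 33.3% | 2/6 = 33.3% | 2/4 = 50.0% |

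The absolute gap, k/(6 − u) − k/6, depends on k:
- u = 1: from 3.3 points (k = 1: 20.0% against 16.7%) to 16.7 points (k = 5: 100% against 83.3%).
- u = 2: from 8.3 points (k = 1: 25.0% against 16.7%) to 33.3 points (k = 4: 100% against 66.7%).

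**Effect when k = 0**

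The percentage is 0% for any denominator. Only an upper confidence bound would move, and the visible plan does not call for one. The exact one-sided 95% bound is 1 − 0.05^(1/n):
- n = 6: 39.3%
- n = 5: 45.1%
- n = 4: 52.7%

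**Exposure implied by the table heading**

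The chance of seeing at least one case of an event with true risk p among n dosed patients is 1 − (1 − p)^n. For p = 10%, 20% and 30% it is 46.9%, 73.8% and 88.2% with n = 6, and 41.0%, 67.2% and 83.2% with n = 5. A reader who took six as the number exposed when it was five would credit the study with somewhat more ability to detect harm than it had.

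**The case against.** The strongest case on the other side is that the situation may never occur. Sections 5.1 and 5.3.2 intend every eligible patient to receive afamelanotide. Screening takes place on Day 0, the criteria are checked that day before dosing, and the partly redacted Section 5.3.3 visibly carries a 24-hour limit from symptom onset. The interval between enrolment and first dose is probably short. This stands, and it is why the point is conditional. But a statement of intent is not a population rule, and no visible text removes an undosed patient from the Safety Population.

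Second, the text that would fix the moment of enrolment may be redacted. The content of Section 5.2.3 (Recruitment Management) is not visible, Sections 5.5.1.1 and 5.5.1.2 are blacked out, and Section 5.1 and the TEAE list have gaps. If enrolment is defined there as first administration, the two sets coincide and the point falls. This also stands. What can be said is that the visible wording of Section 5.7.5.1 carries no dosing condition.

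Third, the planned tables are mainly counts and listings (Sections 5.5.3.2 and 5.7.5.8), and counts do not change. The denominator enters only through the word incidence in Section 5.7.3.1 and the population named in Section 5.7.5.7. No visible test, threshold or stopping rule uses the percentage. In a six-patient open-label study, individual listings would also show who was not dosed. All of this limits the consequence, but it does not make the definition right for an endpoint that the plan itself calls an incidence.

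**Conclusion.** The concern holds as a minor, conditional point. As written, the primary incidence equals the incidence among dosed patients multiplied by (6 − u)/6. There is no effect if all six are dosed, a relative understatement of 16.7% if one is not, and 33.3% if two are not. With no TEAEs the percentage is unaffected. The size rests on assumed values of u, on reading incidence as a proportion of the Safety Population, and on no redacted text equating enrolment with first dose. Counts of affected patients are correct in every case, and no visible decision depends on the percentage.

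**What to change.** In Section 5.7.5.1, define the Safety Population as all patients who receive at least one administration of afamelanotide. List patients who were enrolled but not dosed separately, together with any pre-dose serious adverse events, which Section 5.7.5.8 already requires the study report to document. No safety information is lost, because that section also lists all adverse events, including those that are not treatment-emergent.

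The cost is one sentence, with no new data, visits or patients. The only drawback is that the safety denominator may fall below six, and it would then be the true number exposed.
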